Aim 1: Establish the feasibility and acceptability of Caring Cards for Veteran card makers and recipients (i.e., 70% average group attendance, > 75% average satisfaction with group participation and card receipt, and 70% average follow-up response). Establish feasibility and acceptability for optional meetup groups (i.e., 70% average meetup group attendance [feasibility] and > 75% average satisfaction with meetup groups [acceptability]).

Aim 2: Evaluate pre/post changes in thwarted belongingness and perceived burdensomeness among card-makers and recipients.

Aim 3: Evaluate pre/post changes in social connectedness and suicide risk among card makers and recipients.

Section 7 - Background and Significance

7) Provide a succinct discussion of relevant background information to justify performing the proposed study.

Veteran suicide is an epidemic; from 2005-2016, suicide rates have risen 26% despite increased prevention efforts. Suicide prevention is VA's highest priority. Efforts to expand and develop innovative services are required to address this ever-growing problem. Thwarted belongingness and perceived burdensomeness are potent transdiagnostic social risk factors for suicide. Unfortunately, few interventions have directly targeted these constructs to reduce suicide risk. The overarching goal of this project is to refine and evaluate Caring Cards, an innovative peer-centered intervention that aims to reduce suicide risk by promoting social recovery among Veterans. Inspired by caring contacts for suicide prevention and the recovery model, Caring Cards employs a novel approach to social recovery by leveraging Veterans' lived experience with mental health conditions. In Caring Cards, Veterans compose messages of hope and unity by handmaking one-of-a-kind cards in outpatient groups. These cards are then sent to their anonymous peers who identified to be at elevated risk for suicide.

In a recent pilot study conducted by [name] and colleagues (IRB #H190032), preliminary data indicate Caring Cards is highly feasible and acceptable to both Veteran card makers and recipients. These data also suggest Caring Cards benefits both Veteran card makers and

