We plan to recruit a total of 80 participants- 30 Veterans with inactive high-risk flags (HRFs) for suicide will be recruited to serve as the Caring Cards group members (i.e., card makers), and 50 Veterans with active HRFs will be recruited to serve as our card recipients. We have developed a targeted/planned enrollment specifically to ensure the inclusion of **women** and racial/ethnic **minorities**. The VA San Diego serves a diverse population of Veterans, including by gender, ethnicity,

age/era and mental health and physical diagnoses. Recent data indicate that 15% of the Veterans accessing the clinic were females and 14% were African-American and 11% were Hispanic/Latino. We will systematically monitor the gender and ethnic composition of the screened and recruited sample and contrast proportions with known gender and ethnic composition of Veterans on the inactive and active high-risk for suicide list. Should substantial discrepancies present (>10%) in regard to the rate of those screened or enrolled compared to the anticipated rate, our investigative team will review procedures and identify potential remedies. Children (persons under the age of 18) will not be recruited into the study.

Recruitment: The VASDHS keeps record of all Veterans with inactive and active HRFs. A waiver of HIPAA authorization will be obtained in order to extract CPRS contact information (i.e., mailing address and telephone number) of Veterans with inactive and active HRFs. The study coordinator will mail a letter to prospective participants introducing the study (see letter attached to protocol submission). Per standard protocol, two weeks after the letter is sent, the study coordinator will contact the prospective participants by phone and invite them to be screened for potential study enrollment.

For inpatient prospects, the study coordinator will consult with the PI and/or the Veteran's treating inpatient teams to determine the appropriate timing of approaching Veteran on the unit. If appropriate, the study coordinator will conduct screening on the unit, and if agreeable to participate, consent and baseline assessments may be completed prior to or following discharge.

In our original protocol, we were approved to recruit participants by mailing them an introductory letter followed by a telephone call two weeks after the letter.

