If a Veteran is conservated, the study coordinator will obtain their conservator's consent for study enrollment, as well as the assent of the conserved Veteran.

Caring Cards Groups (Veteran card makers with inactive HRFs): Our study will include three groups, each with 10 Veterans; they will meet separately for 120 minutes once per week at the VASDHS for six months. If groups are unable to take place in-person due to COVID-19 precautions, groups will take place using the VA-approved virtual platform, WebEx. Groups will be facilitated by a post-doctoral or intern-level therapist supervised by the PI, who is a licensed clinical psychologist. If groups are unable to meet in-person, art supplies and cards will be mailed to the group members at their mailing address. If groups take place remotely, this may increase recruitment; however, due to the scope of this pilot project, enrollment will be capped at 10 Veterans per group (a total of 30 card makers). Group members will be assessed for suicide risk at enrollment and follow-up. In addition, the groups' facilitator will remind Veterans at the start of each group to please let them know before the end of group if they are experiencing any thoughts of suicide or homicide. If group is conducted virtually, the Veteran may ask the facilitator to call them after the group has concluded. If suicide is reported, the group's facilitator will further assess their risk by completing a C-SSRS; if the Veteran's C-SSRS is positive, the facilitator will contact the PI for further risk assessment and Safety Planning.

Sending Caring Cards (Veteran card recipients with active HRFs): A total of six cards, one per month, for six months will be mailed. Veterans recruited from psychiatric inpatient care will be mailed a card within the week following their discharge; cards will be sent on a monthly basis thereafter. This is consistent with post-discharge caring contacts recommendations. The study coordinator will contact Veterans via phone two weeks after the card was sent to confirm they received it. Because card-recipients are receiving regular contact by VA Suicide Prevention Coordinators and will receive formal suicide risk assessment at enrollment and follow-up, they will not be directly assessed for suicide risk following the mailing of each card.

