Optional Meet-Up Groups (card makers and recipients): All study participants will be invited to attend one or more monthly, 120-minute optional, unstructured meetup groups at the VASDHS facilitated by a therapist. A total of four meet-up groups will be offered throughout the study's duration. Again, if COVID-19 precautions are in effect and these groups cannot meet in person, they will be invited to meet via WebEx. Meet-up groups will begin with an introduction to the purpose of the group (i.e., the facilitator will explain that this is an opportunity for the card makers and recipients to meet one another) followed by a review of basic group rules (i.e., limits of confidentiality will be reviewed, group members will be informed that they are free to come and go as they please, meaning they can arrive later than the designated start time and leave earlier than the end time, and the facilitator will be available if anyone has any questions or concerns). The facilitator will remind meet-up group attendees that if they are having thoughts of suicide or homicide, they should speak directly to them. If group is conducted virtually, the Veteran may ask the facilitator to call them after the group has concluded. If suicide is reported, the group's facilitator will further assess their risk by completing a C-SSRS; if the Veteran's C-SSRS is positive, the facilitator will contact the PI for further risk assessment and Safety Planning.

Follow-up Assessments: All follow-up assessments will be collected in-person or via remote methods described above by the study coordinator.

Follow-up assessment battery includes: Beck Scale for Suicidal Ideation (BSS), C-SSRS "Since Last Contact," Interpersonal Needs Questionnaire (INQ-15), NIH Toolbox Adult Social Relationship Scales, and Intervention Satisfaction Questionnaire (developed by PI).

Card makers: Veterans are expected to participate in the Caring Cards groups for six months. Follow-up assessments will be collected within one month of the last group meeting. If a card maker drops out prior to the group's end date, follow-up will be collected within one month the last group meeting they attended. **Card recipients:** Follow-up assessments will be collected within one month after the delivery of the final card. If a card recipient drops out prior to this, follow-up will be collected within one month after the last card they received.

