Feasibility & Acceptability: Feasibility for card makers will be assessed by the proportion of enrolled Veterans who attend all scheduled Caring Cards groups. Feasibility for recipients will be assessed by the ratio of cards sent and received. For all participants, feasibility will be measured by the proportion of Veterans 1) referred for screening, 2) determined eligible, 3) enrolled /completed baseline, and 4) complete follow-up assessments. Feasibility of the optional meet-up groups will also be evaluated based on average attendance. Acceptability for all participants will be assessed by the Intervention Satisfaction Questionnaire, a measure that will be developed by the research team to assesses Veterans' satisfaction with their participation in the Caring Cards and meet-up groups (if attended), as well as asks for feedback about Caring Cards and assesses reasons for study dropout or non-attendance to meet-up groups.

Participant Compensation: Participants will be paid a total of \$120 to complete the baseline and follow-up assessment (\$60 each). No recruitment will take place year two. We would like to pay participants \$120 at baseline, or \$60 at each assessment (baseline and follow-up).

Fidelity: For groups, Caring Cards is a manualized intervention and the facilitator (trained by the PI) will run the groups. The PI will review audiotapes of treatment delivery using a fidelity rating scale, and feedback will be shared in weekly supervision. To assess fidelity for sending cards, quantity, timing, and receipt of the cards will be recorded by the study's research assistant. The study coordinator will monitor the accuracy of this record.

In our original protocol we were approved to use VA-approved audio recording devices to record the groups to ensure fidelity. Given that some groups are likely to take place via telehealth, we would like to amend our protocol to include recording groups via WebEx. VA WebEx has a recording features and for all telehealth groups, we propose to use this feature to record the sessions. The recordings of these WebEx groups will be stored via within the VA WebEx account used to facilitate the group. These recordings will be stored via password protection behind VA firewall and encrypted VA-specific WebEx account (i.e., veteransaffairs.webex.com). Only study personnel will have access to these recordings.

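### Recipient feasibility is judged on cards sent and received, so any cards left unsent after dropout fall outside the measure, which can then read near 100% although much of the six-card course was not delivered

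*Protocol*

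**What the plan says.** The recipient measure is in the protocol, Section 9, under Feasibility & Acceptability: "Feasibility for recipients will be assessed by the ratio of cards sent and received". The same paragraph measures card makers differently, as the share of those enrolled who come to every scheduled group. For both cohorts it adds the proportions referred, eligible, enrolled and, last, those who "4) complete follow-up assessments".

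The planned exposure is in Section 9 under Sending Caring Cards: "A total of six cards, one per month, for six months will be mailed". The cohort size is given at the start of Section 9: "50 Veterans with active HRFs will be recruited to serve as our card recipients". Receipt is established by telephone: "The study coordinator will contact Veterans via phone two weeks after the card was sent to confirm they received it".

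Early dropout is foreseen in Section 9 under Follow-up Assessments: "If a card recipient drops out prior to this, follow-up will be collected within one month after the last card they received".

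Aim 1 in Section 6 sets these criteria: "70% average group attendance, > 75% average satisfaction with group participation and card receipt, and 70% average follow-up response". It adds separate targets for the optional meet-up groups. None of them counts cards.

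Under Fidelity, Section 9 says: "To assess fidelity for sending cards, quantity, timing, and receipt of the cards will be recorded by the study's research assistant". Section 27.4b2 lists the mailing dates among the items held in the study database.

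**The concern.** A feasibility measure for a six-month course should fall when people do not get the course. Received over sent does not do so if mailing ends with dropout. It answers whether a posted card arrives, not whether six monthly cards can be delivered to Veterans with active flags. A recipient who leaves after one card scores 1/1, the same as one who receives all six at 6/6.

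The treatment of the two cohorts is uneven. A card maker who leaves early counts against feasibility, because the reference is enrolled people and scheduled groups. A recipient who leaves early need not count at all. Recipients are the larger cohort, 50 of 80. Section 7 presents feasibility in these new populations as a step to be taken before the effect on suicide risk is assessed, so a flattering recipient figure would mislead on the question that the study is meant to settle first.

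**Working it through.** The protocol states no numerical value for this measure, so there is no figure to reproduce. The check is direct arithmetic.

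**Inputs from the protocol (Section 9)**
- Recipients: 50
- Cards scheduled per recipient: 6
- Cards scheduled in all: 50 x 6 = 300

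**Inputs assumed, because the protocol gives none**
- D, the number of recipients who drop out: 5 to 25 of 50
- k, the cards each dropout was sent before leaving: 1 to 3
- r, the share of mailed cards confirmed received: 95% or 100%
- Mailing stops at dropout

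**Formulas**
- Sent = 6 x (50 - D) + k x D
- Received = r x sent
- Stated ratio = received / sent = r, whatever D and k are
- Ratio on the planned course = received / 300

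The third line is the main result: given that mailing stops, the stated ratio cannot respond to dropout. The assumptions about D and k affect only the size of the gap. The protocol does not say which count is the denominator. Inverting the ratio changes nothing here, since unsent cards are in neither count.

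**Results**

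| D | k | r | Sent | Received | Received / sent | Received / 300 |
|---|---|---|---|---|---|---|
| 5 | 3 | 100% | 285 | 285 | 100% | 95.0% |
| 10 | 1 | 100% | 250 | 250 | 100% | 83.3% |
| 20 | 2 | 100% | 220 | 220 | 100% | 73.3% |
| 20 | 2 | 95% | 220 | 209 | 95% | 69.7% |
| 20 | 1 | 100% | 200 | 200 | 100% | 66.7% |
| 20 | 1 | 95% | 200 | 190 | 95% | 63.3% |
| 25 | 1 | 100% | 175 | 175 | 100% | 58.3% |

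Worked line: with D = 20 and k = 1, sent = 6 x 30 + 1 x 20 = 200. With r = 100%, the stated ratio is 200/200 = 100% and the planned-course ratio is 200/300 = 66.7%.

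**If mailing does not stop.** When all six cards go to everyone, sent = 300 and the two ratios are identical.

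**Can other planned measures show the shortfall?** Referral, eligibility and enrolment come before the first card. Follow-up completion may pick up attrition, but dropouts are themselves to be followed up after their last card. A recipient who had one card and completed follow-up therefore counts as a success on that measure. If instead all 20 dropouts in the illustration skipped follow-up and everyone else responded, recipient response would be 30/50 = 60%, below the 70% criterion. Satisfaction describes acceptability, not delivery.

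**The case against.** The strongest objection is that the premise is inferred. The sentence on sending cards says without condition that six will be mailed, and the wording on a dropout's last card only times the follow-up visit. A recipient need do nothing in order to be sent a card. This stands as a limit on the claim: the stop in mailing is the natural reading of a last card that precedes the final one, but it is not a stated rule.

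Second, loss of contact is not the same as withdrawal. If cards still go to a Veteran who no longer answers the telephone, they count as sent but unconfirmed, and the stated ratio does fall. This also stands. Readings near 100% need dropouts whose mailing ended and mailed cards that were nearly all confirmed.

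Third, a reader might infer that a failure to deliver cards could never make Aim 1 fail. The documents do not support that. The follow-up and satisfaction criteria reach recipients, and the 60% case above shows one route by which attrition could register. What remains true is that no criterion measures delivery, and the indirect signals are not assured.

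Fourth, Section 7 frames the recipient question as whether cards can be sent and feedback collected, and card quantity and receipt are recorded under Fidelity. A shortfall could therefore be found in the data. That makes the better measure easy to compute, but it does not make it the feasibility measure.

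Fifth, the denominator might be thought a detail for the statistical analysis plan, which is not at hand. Direction and pooling could well be left there. But the protocol itself names the two counts to be compared, and neither refers to the six scheduled cards.

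Finally, the illustrations need substantial dropout to look alarming. With every mailed card arriving, 18 dropouts after card 1 give 210/300 = 70.0% and 19 give 205/300 = 68.3%. For dropouts after card 3, more than 30 of 50 would have to leave before the figure fell below 70%. This is a fair caution about size.

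**Conclusion.** The point holds in a conditional form. As defined, the recipient measure is the receipt rate among mailed cards. If mailing ends at dropout, it does not respond to attrition and can read 95% to 100% while delivery of the planned course is far lower. In the cases tabulated, delivery runs from 95.0% down to 58.3% of 300 cards. The size rests on assumed dropout, timing and confirmation rates; the insensitivity does not depend on those rates, only on mailing having stopped.

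Two further inferences should not be drawn. The protocol does not fix 70% as a benchmark for cards; that figure belongs to attendance and follow-up, and is used here only for comparison. Nor does an unconfirmed card show non-delivery, since it may reflect an unanswered call. The change is nevertheless worth making: it replaces a stated measure with a more informative one, uses data already collected, and gives the same answer if all six cards are always mailed.

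**What to change.** In Section 9, define recipient feasibility as cards confirmed received divided by cards scheduled, at six per enrolled recipient (300 if 50 enrol). This puts recipients on the enrolled-and-scheduled basis already used for card makers. Keep received over sent as a secondary figure for postal fidelity, and state its direction.

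Report the shortfall in two parts: cards sent but not confirmed, and cards never sent. Telephone non-response is then not mistaken for non-delivery.

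State whether mailing continues after a recipient drops out, so that the sentence on six cards and the sentence on the last card can be read together. Which of the two applies is for the investigators to say.

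If Aim 1 is to carry a benchmark for this measure, the investigators should set it in advance; 70% is one option, and the change of denominator does not depend on it.

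The cost is wording in Section 9 and, if a benchmark is added, in Aim 1. No new data and no extra contact with participants are needed, because mailing dates, quantity and receipt are already recorded. The downside is that the reported figure may be less favourable.

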Monitoring of Suicidal Ideation: This is a challenging aspect the study and so we have developed our procedures to be consistent with the recommendations of organizations such as NIH in clinical research in people with elevated suicide risk (e.g., Issues to Consider in Intervention Research with Persons at High Risk for Suicidality). We will further refine our procedures by use of deployment focused discussions with stakeholders in the study start up phase and in collaboration with the Data Safety Monitoring board. The referral sources for this study are VASDHS' Veterans with inactive and active high-risk suicide flags. Veterans with active high-risk suicide flags are closely monitored and regularly assessed for suicide risk by the VASDHS' Suicide Prevention Coordinator (SPCs). At baseline, participants are administered the C-SSRS55. Veterans are informed during consenting that all suicidal behavior is documented in Suicide Behavior Reports in CPRS if not already entered. If ideation exceeds a score of 2, the PI will be contacted and will perform a telephone evaluation and refer the screened potential participant to the SPCs or emergency services as necessary. Our safety monitoring guide details these procedures, how they are recorded, and what the staff, facility, and investigator responsibilities are. All Veterans are provided the contact information for the Veterans' Crisis Line. Any new suicidal behavior will be documented in the Suicide Behavior and Overdose Report in CPRS by research staff. Participants who elect to withdraw from the study will continue to receive suicide prevention services per VA San Diego's protocol. We will monitor these protocols during the course of the study and will make adjustments to inclusion/exclusion criteria or safety protocol in case of adverse events.

All research personnel will complete VA TMS trainings pertinent to suicide prevention.

Confidentiality: In order to protect confidentiality, all participant data will be de-identified by

assigning each participant a unique ID in computer files, and all physical files from the study will be kept in a locked cabinet in study offices at the Veterans Medical Research Foundation building in San Diego. All electronic data and files will be stored on a secure server. Only study investigators and personnel will have access to these data. All documentation will identify participants only by their Unique ID number and not other personally identifying information.

Section 9.11 Pictures and Audio/Video Recordings of Patients

9.11) Describe the purpose of photographs (facial), or audio, or video recordings of patients. Describe whether the recordings will contain, or potentially contain, identifiers. Note: use of photographs or recordings must be covered in the informed consent process and documented consent documents (e.g., consent form, information sheets, telephone screen scripts).

To ensure fidelity of the Caring Cards groups, the PI will review audiotapes of the group leader's treatment delivery using a fidelity rating scale; feedback will be shared with the group leader in weekly supervision. Audio recordings of the Caring Cards groups will contain Veterans speaking; Veterans in the group may say the names of one another; however, other identifying information (e.g., SSN) will likely not be shared out loud by group members.

The delivery of the assessments (baseline and follow-up) will also be audio recorded for quality assurance and fidelity.

In our original protocol we were approved to use VA-approved audio recording devices to record the groups to ensure fidelity. Given that some groups are likely to take place via telehealth, we would like to amend our protocol to include recording groups via WebEx. VA WebEx has a recording features and for all telehealth groups, we propose to use this feature to record the sessions. The recordings of these WebEx groups will be stored via within the VA WebEx account used to facilitate the group. These recordings will be stored via password protection behind VA firewall and encrypted VA-specific WebEx account (i.e., veteransaffairs.webex.com). Only study personnel will have access to these recordings.

Section 9.12 Off Station Activities

9.12) Describe each off-station activity including where it occurs, subject involvement, and any additional required protections. Note: if the off-station activity is being conducted under the approval authority of another institution, this is not VA offsite research and should be described as collaborative research effort. Please contact the HRPP office if you have any questions

Off-station activities will only apply if COVID-19 precautions are still in effective and participants cannot safely participate in the study in-person.

In this case, off-station activity (e.g., Veterans' homes) will refer to: 1) Caring Cards group participation via WebEx, 2) optional meet-up groups via WebEx, and 3) collection of assessments via phone, VVC, or WebEx.

Section 10 - Human Subjects

10) Describe the characteristics of the proposed subject population. Include age, gender, ethnicity, and health status as appropriate. Note: Data about people are still considered "human subjects" by the IRB, so even if you do not intend to contact the patients whose charts you will review, you still describe the characteristics related to the subjects whose charts you will review.

- Provide inclusion and exclusion criteria as appropriate. Provide a statement how non pregnancy is confirmed if pregnancy is an exclusion criteria.
- For multisite studies, provide the total number of subjects from all sites and include description of the local site's role as a coordinating center if applicable.
- Indicate the number of VA participants to be studied.
- Indicate the estimated number of consented subjects that will fail the screening process, if any.

The subject population in this study will be a total of 80 male and female Veterans (30 with

inactive high-risk suicide flags and 50 current high-risk suicide flag). Potentially eligible participants will be screened by research staff. Our inclusion and exclusion criteria were selected in order to increase the generalizability of our sample and broad reach. Participants will be of either gender and any race/ethnicity, decisional capacity, and at least 18 years of age. Complete Inclusion/Exclusion Criteria are as follows:

Inclusion criteria for card makers: (1) VASDHS Veteran with an inactive HRF, (2) 18 years of age or older, (3) access to transportation to attend the group, and (4) decisional capacity.

Inclusion criteria for card recipients: (1) VASDHS Veteran with an active high-risk flag, (2) 18 years of age or older, and (3) decisional capacity.

Exclusion criteria for all participants : (1) the absence of a mailing address or working phone number, (2) inability to read and write in English, (3) previous or current experience as either a card maker or recipient (in original pilot project), and (4) currently employed by the VA San Diego.

If COVID-19 precautions are in effect, Veterans will also be screened for access to reliable computer, tablet, or smartphone with camera and internet access, as well as the willingness to participate in this study remotely. Participants' decisional capacity for informed consent in order to meet eligibility for this study will be assessed during consent (separate from screening call) via the University of California San Diego Brief Assessment of Capacity to Consent (UBACC) will be collected by the study coordinator.

Section 10.2 Pregnant Women

10.2a) Are pregnant women the focus of the research?

Yes No

10.2b) Provide the justification for including pregnant women and address any special risks, protections, and safeguards.

Being pregnant is not an exclusion criterion for this study; they are not an explicit focus of this research. There are no risks associated with this study that would apply specifically to pregnant women.

Section 11 - Recruitment

11) Describe, step-by-step, the plans for recruitment of subjects (or selection of subjects as in record review). This description must include how, when, and where potential subjects are approached as well as procedures for identifying potential participants (through medical records, physician referral, third-party sources, etc.). Include how selection is equitable. Indicate if vulnerability to coercion may be present and if so plans to ensure voluntary participation.

Recruitment: The VASDHS keeps record of all Veterans with inactive and active HRFs. A waiver of HIPAA authorization will be obtained in order to extract CPRS contact information (i.e., mailing address and telephone number) of Veterans with inactive and active HRFs. A letter to prospective participants introducing the study (see letter attached to protocol submission) will be sent. Letters to Veterans with inactive HRFs will be sent by the Chief of Psychology, [name], who is a co-I of this project. Letters sent to Veterans with active HRFs will be sent by their Suicide Prevention Coordinators who are in regular contact with HRF Veterans (via phone and mail). Per standard protocol, two weeks after the letter is sent, the study coordinator will contact the prospective participants by phone.

For inpatient prospects, the study coordinator will consult with the PI and/or the Veteran's treating inpatient teams to determine the appropriate timing of approaching Veteran on the unit. If appropriate, the study coordinator will conduct screening on the unit, and if agreeable to participate, consent and baseline assessments may be completed prior to or following discharge.

In our original protocol, we were approved to recruit participants by mailing them an introductory letter followed by a telephone call two weeks after the letter.

We would like to amend our approach by including recruiting participants via their providers. Specifically, we would like to approach VA healthcare providers/clinics (e.g., Primary Care Mental Health Integration, Center of Recovery Education, Mood Clinic, PTSD Clinic), with information about the study, asking them to share this information with their Veterans.

Providers will share study information verbally and/or via study flyer (see below) with Veterans during their standard clinical interactions. If a Veteran is interested in learning more about the study, providers will ask their permission to have our study personnel reach out to them to discuss screening/enrollment. Providers will alert study personnel to interested Veterans via encrypted VA email or adding them as additional signers to Veterans' CPRS progress notes.

Last, providers will inform Veterans that they can directly reach out to our study personnel if they are interested in participating. Contact information for personnel will be provided on our study flyer described below.

To facilitate recruitment via providers, we would like to share a study flyer with providers/clinics so they can distribute to their Veterans. Please see attached for a draft of our flyers – one for card makers and one for card recipients. Moreover, we have an information flyer for providers, which we have included as well.

Section 11.1 Recruitment Materials

